## PROTOCOL AMMENDMENTS

| Protocol Version  | Issue Date  |
|-------------------|-------------|
| Original Protocol | 17-Jan-2018 |
| Amendment 1       | 02-Jul-2018 |

### Amendment\_1 (02-Jul-2018)

**The overall reason for the amendment:** the overall reason for this amendment was to provide clarification to the existing inclusion criteria with definition of Inadequate response, dose, duration of partial responder and time period of assessment for patients with Ankylosing Spondylitis and Psoriatic Arthritis as suggested by DCGI.

| Applicable Section(s)  | Description of Change(s)   |
|--|--|
| Rationale: As requested by the DCGI, definition of inadequate response, dose, duration of partial responder and time period of assessment for patients with Ankylosing Spondylitis was provided as a clarification to the existing inclusion criteria for Ankylosing Spondylitis. |  |
| Synopsis;
4.1 Inclusion Criteria  | Patients with Ankylosing Spondylitis, having an Inadequate response (defined as BASDAI $\geq 4$ ) to current or past therapies (including biologics naïve patients). Patients who were receiving NSAIDs or DMARDs had to have received continuous therapy for 3 months at the highest recommended doses or had to have been unable to receive a full 3-month course of full-dose NSAID or DMARD therapy because of intolerance, toxicity, or contraindications. Maximum recommended dosages for DMARDs if used, would be: methotrexate 25 mg/week, oral corticosteroids ( $\leq 10$ mg/day of prednisone or equivalent) or sulfasalazine 3 g/day.  |
| Rationale: As requested by the DCGI, definition of inadequate response, dose, duration of partial responder and time period of assessment for patients with Psoriatic Arthritis was provided as a clarification to the existing inclusion criteria for Psoriatic Arthritis.       |  |
| Synopsis;
4.1 Inclusion Criteria  | Patients with Psoriatic Arthritis, having an inadequate response (defined by presence of active arthritis [presence of any swollen or any tender joint]) despite current or previous therapies (including biologics naïve patients). Patients who were receiving NSAIDs or DMARDs had to have received continuous therapy for 3 months at the highest recommended doses or had to have been unable to receive a full 3-month course of full-dose NSAID or DMARD therapy because of intolerance, toxicity, or contraindications. Maximum recommended dosages for DMARDs, if used would be: methotrexate 25 mg/week, oral corticosteroids ( $\leq 10$ mg/day of prednisone or equivalent), sulfasalazine 3 g/day or leflunomide 20 mg/day. |

## STUDY SYNOPSIS

A Phase-IV, Multicenter, Noncomparative, Open-Label Study Evaluating the Safety and Efficacy of Golimumab (a Fully Human Anti-TNF $\alpha$  Monoclonal Antibody, Administered Subcutaneously) in the Treatment of Indian Patients with Active Spondyloarthropathy of Ankylosing Spondylitis or Psoriatic Arthritis

The term "sponsor" used throughout this document refers to the entities listed in the Contact Information page(s), which will be provided separately.

Golimumab is a human monoclonal antibody that binds to both the soluble and transmembrane bioactive forms of human tumour necrosis factor  $\alpha$  (TNF $\alpha$ , a cytokine protein). This interaction prevents the binding of TNF $\alpha$  to its receptors, thereby inhibiting the biological activity of TNF $\alpha$ . Golimumab antibody does not bind to other TNF superfamily ligands, including human lymphotxin. Golimumab does not lyse human monocytes expressing transmembrane TNF in the presence of complement or effector cells. Elevated TNF $\alpha$  levels in the blood, synovium, and joints have been implicated in the pathophysiology of several chronic inflammatory diseases such as rheumatoid arthritis, psoriatic arthritis (PsA), and ankylosing spondylitis (AS).

Post-marketing Phase IV clinical trial is useful in identifying new safety issues and trends, which were not observed in previously conducted controlled clinical studies. The data obtained from the present study will help to understand the safety and efficacy profile of golimumab in a real-world Indian scenario compared with that obtained in a controlled clinical environment.

The objective of the present study is to address the mandatory regulatory requirement of Indian Health Regulatory Authority (Drugs Controller General of India [DCGI]) regarding conduct of study in Indian population to monitor the adverse events (AEs) with SIMPONI® (golimumab 50 mg) in patients of AS or PsA with active disease. The study will assess the safety of SIMPONI® prescribed as per locally approved prescribing information in Indian patients with active AS or PsA.

## OBJECTIVES

### Primary Objective

- To assess the safety of subcutaneous (SC) golimumab in patients with active AS or PsA over 24 weeks.

### Secondary Objectives

- To assess the efficacy of SC golimumab in patients with active AS or PsA as measured by reduction in signs and symptoms of arthritis in active AS or PsA at Week 14.
- To assess achievement of sustained arthritis response in patients with active AS or PsA at Week 24.

## HYPOTHESIS

No formal hypothesis testing will be conducted.

## OVERVIEW OF STUDY DESIGN

This is an open-label, multicentre, interventional, noncomparative, single-arm, Phase IV study to assess the safety and efficacy of golimumab in Indian patients with active spondyloarthropathy of AS or PsA. Approximately, 100 patients (50 patients of AS and 50 patients of PsA) selected by investigators and determined to be eligible for golimumab treatment per protocol eligibility criteria will be enrolled in the study, after obtaining written informed consent. Patients will be monitored for AEs during 24 weeks of treatment with golimumab and till end of study (EOS) visit (8 weeks after the last dose of golimumab). Participating investigator will be trained on the locally approved prescribing information of golimumab by the sponsor designee before the enrolment of first patient. Commercial stocks of SIMPONI® will be used

for the patients enrolled in the study with appropriate labelling and will be provided free of cost to the patient enrolled for 24 weeks treatment. Patients will procure SIMPONI® from the existing distribution channel (regular supply chain) as obtained by routine patients but the drug will be free of cost for clinical trial patients as per the mentioned duration in the study protocol. Study drug will be administered at the investigator study site by the investigator or an appropriately licensed and authorized health professional (under the supervision of the investigator).

#### Screening Visit (Visit 1 / Day [-7 to -1]):

After obtaining the signed informed consent, data will be collected at this visit including demographics, medical history, disease-related history, concomitant medications, and laboratory investigations.

#### Treatment Visits:

Patients who qualify will be enrolled in the study and will receive the study drug on confirmation of their enrolment status. Patients will receive golimumab 50 mg SC injections at Week 0 and every 4 weeks thereafter through Week 24 (ie Week 0, Week 4, Week 8, Week 12, Week 16, Week 20 and Week 24).

#### Assessment Visit:

This visit will be an additional visit conducted at Week 14. In this visit, all the assessments will be performed for evaluating efficacy endpoints at Week 14.

#### End of treatment (EOT) Visit:

The EOT visit will be conducted after the completion of 24 weeks SIMPONI® treatment (at Week 24) or on the day at which the patient discontinues the SIMPONI® treatment or study.

#### End of Study (EOS) Visit:

End of study visit (in-person or telephonic as per convenience of the patient) will be conducted 8 weeks after the EOT visit or after the last dose of golimumab (whichever is earlier), to inquire about any AEs experienced by the patient. Any clinically significant abnormalities persisting at the EOS/early withdrawal will be followed by the investigator until resolution or until a clinically stable endpoint is reached.

All the study-related activities or procedures of each and every visit of this Phase IV clinical trial are summarized in the TIME AND EVENTS SCHEDULE**Error! Reference source not found.**, presented after the synopsis.

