## 2. OBJECTIVES, ENDPOINTS, AND HYPOTHESIS

### 2.1. Objectives

#### Primary Objective

- To assess the safety of SC golimumab in patients with active AS or PsA over 24 weeks.

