### **3. STUDY DESIGN AND RATIONALE**

#### **3.1. Overview of Study Design**

This is an open-label, multicentre, interventional, noncomparative, single-arm, Phase IV study to evaluate safety and efficacy of golimumab (a fully human anti-TNF $\alpha$  mAb, administered subcutaneously) in the treatment of Indian patients with active spondyloarthropathy of AS or PsA. A total of 100 patients will be enrolled in this study. Approximately, 50% patients would be enrolled for each indication. Enrollment of participants with the diagnosis of AS and PsA will start simultaneously. After enrollment of all 50 participants with one of the disease condition (AS or PsA) the recruitment of participants for that particular disease condition should be stopped, while recruitment for the other disease condition should continue until 50 participants are recruited. Patients will receive golimumab 50 mg SC injections at Week 0 and every 4 weeks thereafter through Week 24. The end of treatment (EOT) visit is defined as the time the last subject completes the Week 24 visit. End of study (EOS) visit (in-person or telephonic as per convenience of the patient) will be conducted 8 weeks after the EOT Visit or after the last dose of golimumab (whichever is earlier), to inquire about any AEs experienced by the patient.

A diagram of the study design is provided below in Figure 1

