### **10.2. Discontinuation of Treatment**

If a patient must be discontinued from treatment before the EOT regimen, this will not result in automatic withdrawal of the patient from the study.

A patient should be discontinued from study treatment if:

- The investigator believes that for any safety reasons (ie, AE) as mentioned below, it is in the best interest of the patient to stop treatment:
  - opportunistic infection
  - malignancy, excluding nonmelanoma skin cancer
  - CHF
  - demyelinating disease
  - subject is deemed ineligible according to the TB screening criteria
- The patient becomes pregnant.
- The patient initiates the use of prohibited medications or treatments.

- The patient develops a severe or serious injection-site reaction or serious infection.
- Noncompliance defined as any missed visit which results to missed doses. The investigator should contact the medical monitor to discuss any unexplained study drug non-compliance.

If a patient discontinues treatment before the EOT, all Week 24 evaluations should be performed.

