2.6. Handling Missing Data

For subjects who discontinue treatment but continue to be followed up and for whom some endpoint component data are missing, the last observation carried forward will be followed to Week 14 or Week 24 as applicable.

For a composite endpoint, if all its components are missing, no imputation will be done; if not all its components are missing, LOCF will be used to impute the missing components.

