3.2. Disposition Information

Disposition will be summarized for each indication and overall population, separately.

If the patient has completed the EOS assessments (in person or telephonically) then the disposition event of that patient will be considered as “Completed”.

The summary for the treatment disposition will be as follows:

- Number of subjects enrolled
- Number of subjects discontinued the study drug

The Summary for the study disposition will be as follows:

- Number of subjects enrolled
- Number of subjects receiving study drug
- Number of subjects completed the study
- Number of subjects terminated study participation prematurely

The following primary reason for discontinuation will be summarized throughout the study under the following categories:

- Adverse Event
- Death
- Disease Relapse
- Lack of Efficacy
- Lost to Follow-Up
- Non-Compliance with Study Drug
- Received a Disallowed Concomitant Treatment
- Physician Decision
- Protocol Violation
- Study Terminated by Sponsor
- Withdrawal by Subject
- Screen Failure (Failure to Meet Eligibility Criterion)
- Pregnancy
- Progressive Disease
- Other

A listing of subjects will be provided along with the dates, study days and reason for discontinuation/ termination for the following categories:

- Subjects who discontinued study agent
- Subjects who terminated study prematurely

The summary tables and listings will be provided separately for each indication and overall population separately.

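### The end-of-study rule always means last dose plus 8 weeks, so a patient last dosed at Weeks 0 to 12 leaves AE follow-up before Week 24 but stays in the 24-week denominator and is labelled a completer

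*Protocol*

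**What the plan says.** **End of study.** The Synopsis says the EOS visit, in person or by telephone, "will be conducted 8 weeks after the EOT visit or after the last dose of golimumab (whichever is earlier"). The same rule stands in the note under the synopsis visit schedule, Table 1 note k, Protocol 3.1, 9.1.3 and 9.2, and SAP 1.2. The Synopsis design overview places EOS simply 8 weeks after the last dose.

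**End of treatment.** The Synopsis and Protocol 9.1.3 put EOT at Week 24 "or on the day at which the patient discontinues the SIMPONI® treatment or study" (Synopsis wording). Protocol 3.1 has a study-level definition: "The end of treatment (EOT) visit is defined as the time the last subject completes the Week 24 visit".

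**Objective and AE collection.** The primary objective is "To assess the safety of SC golimumab in patients with active AS or PsA over 24 weeks", and the synopsis statistical section describes AE frequency and proportion over the same 24 weeks. Protocol 12.3.1 ends AE reporting at the subject's last study-related procedure. SAP 2.2 keeps every dosed patient in the Safety set. SAP 5.2 reports numbers and percentages of subjects with an event, and treats events as treatment-emergent up to 8 weeks after the last dose.

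**Patients who stop early.** Protocol 10.2 says of early discontinuation that "this will not result in automatic withdrawal of the patient from the study". It also asks for the Week 24 evaluations in these patients, without saying when. Among its reasons to discontinue is "Noncompliance defined as any missed visit which results to missed doses". SAP 2.6 carries the last observation forward to Week 14 or 24 "For subjects who discontinue treatment but continue to be followed up".

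**Completion.** SAP 3.2 states: "If the patient has completed the EOS assessments (in person or telephonically) then the disposition event" is *Completed*. Protocol 10.1 is to the same effect. Neither sets a minimum length of follow-up.

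**The concern.** The rule reads as a choice between two anchors, but only one can ever apply. For a patient who takes all seven doses this makes no difference. For a patient who stops early it moves the last contact, and with it the end of routine AE collection, to before Week 24.

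The primary result is a set of AE percentages presented as 24-week figures. If some patients in the denominator were observed for 8, 12, 16 or 20 weeks, the percentages mix unequal observation times. The SAP plans no summary of follow-up duration and no exposure-adjusted rate that would show this. The *Completed* label hides it further: a patient with one dose and a Week 8 telephone call qualifies. Events that appear late are the ones most exposed, and Protocol 9.2 specifically asks for serious infections (including TB) and malignancies to be summarised.

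**Working it through.** **1. Inputs.** Dose visits are on Days 1, 28, 56, 84, 112, 140 and 168 (Weeks 0 to 24 by fours; Protocol 7 and Table 1). EOS is the smaller of EOT + 56 days and last dose + 56 days. The objective's horizon is Week 24, Day 168.

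**2. Reproduce the plan's own figure.** With all seven doses, last dose and EOT are both Day 168, and 168 + 56 = Day 224. This matches the Week 32 visit in Table 1.

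**3. Which branch applies.** EOT is either the Week 24 dosing visit or the day of discontinuation, so EOT is on or after the last dose. Under the study-level definition in Protocol 3.1 it is also no earlier than any patient's last dose. Hence min(EOT + 56, last dose + 56) = last dose + 56. As a check, for each early last dose every EOT day from that dose to 8 days past the next dose visit was tried; there was no exception.

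**4. EOS by last dose** (nominal days):

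| Last dose | EOS | Weeks short of Week 24 |
|---|---|---|
| Week 0 (Day 1) | Day 57, Week 8 | 24 − 8 = 16 |
| Week 4 (Day 28) | Day 84, Week 12 | 24 − 12 = 12 |
| Week 8 (Day 56) | Day 112, Week 16 | 24 − 16 = 8 |
| Week 12 (Day 84) | Day 140, Week 20 | 24 − 20 = 4 |
| Week 16 (Day 112) | Day 168, Week 24 | 0 |
| Week 20 (Day 140) | Day 196, Week 28 | 0 |
| Week 24 (Day 168) | Day 224, Week 32 | 0 |

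With the ±4-day windows on both dose and EOS, a Week 12 last dose gives EOS on Days 132 to 148, still before Day 168. A Week 16 last dose gives Days 160 to 176, so it can fall up to 8 days short.

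**5. What the AE tables then contain.** The treatment-emergent window in SAP 5.2 also ends at last dose + 8 weeks. A one-dose patient contributes 8 weeks and a full-course patient 32, each counting as one subject in the same percentage.

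**6. Unobserved time.** Planned observation to Week 24 is 100 × 24 = 2400 patient-weeks. The documents give no discontinuation rate, so this is a range under assumptions. If early last doses are spread evenly over Weeks 0, 4, 8 and 12, the mean loss is (16 + 12 + 8 + 4)/4 = 10 weeks.

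- 5 patients: 5 × 10 = 50, or 2.1% of 2400
- 10 patients: 10 × 10 = 100, or 4.2%
- 20 patients: 20 × 10 = 200, or 8.3%

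The extremes for 5 to 20 patients are 5 × 4 = 20 patient-weeks (0.8%, all last dosed at Week 12) and 20 × 16 = 320 (13.3%, all at Week 0).

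**7. Would changing *earlier* to *later* be enough?** No. If EOT falls at the next dose visit (assumption), EOT + 56 gives Days 84, 112, 140 and 168 for last doses at Weeks 0, 4, 8 and 12. The first three still end before Day 168.

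**The case against.** The strongest reply is that the rule is coherent as a treatment-emergent design. EOS falls exactly where the SAP 5.2 window closes, so by that definition an early stopper's window is fully observed. This stands, but it supports a treatment-emergent percentage, not one described as covering 24 weeks.

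A reader might infer that the primary objective fails for these patients. The documents do not support that. The objective is descriptive and concerns the whole population, and early stoppers remain in the Safety set.

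A reader might also infer that AE incidence is biased downward because patients who stopped for an AE are cut short. Such a patient already counts under any AE; only later or different events can be lost. Abnormalities persisting at EOS and unresolved SAEs are followed further (Protocol 9.2, 12.3.2), and the sponsor evaluates late spontaneous reports (12.3.1). None of this is routine enquiry about new events.

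Third, a reader might estimate the affected share from missed doses: with an assumed 2%, 5% or 10% chance of missing each of the Week 4 to 16 doses, 1 − (1 − q)^4 gives 7.8%, 18.5% or 34.4%. No document gives such a rate. The estimate also supposes that every miss ends treatment, whereas Protocol 10.2 has unexplained non-compliance discussed with the medical monitor, and Protocol 7 simply records missed injections.

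Finally, Protocol 10.2 and the carry-forward rule can be read as keeping stoppers in the study to Week 24, which would limit the problem. Remaining in the study until an EOS contact 8 weeks later is, however, equally compatible with 10.2, and the Synopsis and 9.1.3 put the EOT evaluations on the stopping day. Likewise, *Completed* describes study disposition only: SAP 3.2 separately counts drug discontinuations and lists them with dates and reasons. The one-dose patient is therefore visible as having stopped drug, though not as having short follow-up.

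**Conclusion.** The concern holds as one of truncated, unequal and undisclosed follow-up. It is certain from the dates that the EOT branch never applies and that the EOS rule closes follow-up 16, 12, 8 or 4 weeks before Week 24 for last doses at Weeks 0, 4, 8 and 12. It is equally clear that such patients stay in the AE denominator and become *Completed* once the EOS contact is made.

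That they actually leave before Week 24 follows from the EOS rule but not from every passage. The EOS timing, the two EOT definitions, the Week 24 evaluations after stopping, and the carry-forward wording conflict and must be reconciled.

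The size is unknown. The 2% to 8% of patient-weeks rests on an assumed 5% to 20% early stopping, spread evenly over Weeks 0 to 12. The direct consequence is missed later or additional events in early stoppers and a completion figure that does not mean 24 weeks observed. It is worth correcting because the repair is cheap, not because the primary objective is defeated.

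**What to change.** 1. **Follow-up.** In the Synopsis (design overview, EOS visit and schedule note), Table 1 note k, Protocol 3.1, 9.1.3 and 9.2, and SAP 1.2, set the final AE/SAE contact at Week 24 or 8 weeks after the last dose, whichever is later. Apply it to every treated patient who has not died, withdrawn consent or been lost to follow-up. Telephone contact is already allowed. Align the recording of concomitant medication: Protocol 8 ends it at the last dose, while 9.1.3 asks about it at EOS.
2. **Analysis.** In SAP 5.2, keep the treatment-emergent window but add a summary of all AEs from first dose to Week 24. Without it, the extra events would be collected and then fall outside the treatment-emergent tables. Report follow-up duration or exposure-adjusted rates by indication.
3. **Disposition.** In both Protocol 10.1 and SAP 3.2, show completed treatment and completed AE follow-up to Week 24 as separate lines, and do not count an EOS contact before Week 24 as *Completed*. Changing only the SAP would create a new conflict with the protocol.

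The cost is wording changes in several places, a few extra calls, one extra AE table and a slightly lower completion rate. If follow-up has already ended, item 3 and the follow-up-time reporting in item 2 can still be adopted. No dose or stopping rule changes.

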### **SUBJECT POPULATION**

Patients eligible for the study will be men or women (excluding pregnant or nursing women; men and women planning a pregnancy) aged 18 years or older who have had a definite diagnosis of AS or PsA prior to first study drug administration.

#### Key criteria for AS patients:

Adult patients who have definite diagnosis of AS (according to the Modified New York Criteria) and either have an inadequate response (defined as BASDAI  $\geq 4$ ) to current or past therapies (including biologics naïve patients). Patients who were receiving NSAIDs or DMARDs had to have received continuous therapy for 3 months at the highest recommended doses or had to have been unable to receive a full 3-month course of full-dose NSAID or DMARD therapy because of intolerance, toxicity, or contraindications. Maximum

recommended dosages for DMARDs if used, would be: methotrexate 25 mg/week, oral corticosteroids ( $\leq 10$  mg/day of prednisone or equivalent) or sulfasalazine 3 g/day.

#### Key criteria for PsA patients:

Patients who have definite diagnosis of active PsA (according to the ClASsification criteria for Psoriatic ARthritis [CASPAR]) prior to the first administration of study drug and have at least 1 of the PsA subsets: distal interphalangeal joint arthritis, polyarticular arthritis with the absence of rheumatoid nodules, arthritis mutilans, asymmetric peripheral arthritis, or spondylitis with peripheral arthritis; patients who are negative for rheumatoid factors according to the reference range of the local laboratory conducting the test and have inadequate response (defined by presence of active arthritis [presence of any swollen or any tender joint]) despite current or previous therapies (including biologics naïve patients). Patients who were receiving NSAIDs or DMARDs had to have received continuous therapy for 3 months at the highest recommended doses or had to have been unable to receive a full 3-month course of full-dose NSAID or DMARD therapy because of intolerance, toxicity, or contraindications. Maximum recommended dosages for DMARDs, if used would be: methotrexate 25 mg/week, oral corticosteroids ( $\leq 10$  mg/day of prednisone or equivalent), sulfasalazine 3 g/day or leflunomide 20 mg/day.

Further screening as per inclusion and exclusion criteria will apply.

